Continuous TBS Session: The continuous TBS will be applied using the Cool-B65 A/P coil which has a built in sham system. The Cool-B65 A/P coil is capable of delivering either active or sham rTMS in a manner that is randomized by the system itself and therefore blinded to the treater. The sham setting on this coil looks and sounds similar to the active setting, but has a hidden aluminum plate blocking actual stimulation. The Magventure device holds a blinded key code that is kept by the unblinded CRC. The operator is instructed to flip the coil to correspond with the key code, but does not know the stimulation group (active versus sham).

Stimulation Dose: This study utilizes two applications of 800 pulses of continuous TBS at 80% of the resting motor threshold as this has been demonstrated effective in producing a prolonged change in cortical excitability (30) as well as being demonstrated as safe(17). We will adjust the dose based off of the difference between motor cortex to skull and prefrontal cortex to skull measurements as has been previously reported(92). The spaced application of theta-burst stimulation (TBS) approach was chosen because this study will require more than an hour of modulation of the target in order to complete the scan sessions. The spaced approach has been demonstrated to have a much longer duration of effect than a single 800-pulse cTBS stimulation session(27, 28, 30, 79). The fifteen minute spacing between the two 800-pulse cTBS applications is essential because it has been demonstrated that prolonged stimulation approaches without spacing in between can cause a reversal of intended effect(80).

Stimulation Site: The spaced cTBS approach utilized for this study will be applied to the left dorsolateral prefrontal cortex (L-DLPFC) in the sub-region that has the highest functional connectivity with the dorsal anterior cingulate (dACC). This will be done through the use of neuronavigation hardware coupled with the latest in cutting edge targeting(81). This study will

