Hypnosis Intervention: Hypnosis will be induced while the subject is in the scanner though the use of headphones and a pre-recorded induction script. Hypnotic instructions will be standardized, and will involve a simple induction instruction that has been used in prior research on the brain signature of the hypnotic state (48) as well as in clinical care (94). The instruction includes being asked to: *“Look up and close your eyes, take a deep breath, let the breath out, let your eyes relax, and let your body float, as though you were in a bath, a lake, a hot tub, or floating in space. With your eyes closed and remaining in this state of concentration, enjoy this state of floating relaxation and allow yourself to feel it more and more intensely.”* The ability to enter and maintain the hypnotic state through such an induction mechanism in the fMRI environment has been previously demonstrated in by Oakley, who compared induction using these means in the MRI environment with hypnotic induction “off-line” (95). An extended description of the hypnosis protocol is attached in Appendix 4 (describing hypnotic induction, Hypnotic Induction Profile (HIP), and hypnotic analgesia script).

Randomization and Blinding: Both active and sham rTMS groups will receive simulation from a specially designed coil called the Cool-B65 AP Butterfly coil (Magventure Magpro; Farum, Denmark). This coil is capable of delivering either active or sham rTMS (cTBS) in a manner that is randomized by the system itself and therefore blinded to the treater. The sham setting on this coil looks and sounds similar to the active setting, but has a hidden aluminum plate blocking actual stimulation. The Magventure TMS device holds a blinded key code that is kept by the individual that holds the blind. During the rTMS setup, the operator is instructed to flip the coil to correspond with the key code, but is unclear as to the active versus sham stimulation group.

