9.3 Stimulation Group Assignment Procedures

Stimulation Group Assignment Procedures: Random assignment is a procedure used in experiments to create study groups with similar characteristics so that the groups are equivalent at the beginning of the study. We perform randomization using permuted block to ensure balancing between arms.

Randomization Rationale and Procedure: The *MagLink* software program is used by the principal investigator to define the stimulation protocol for each patient enrolled in the study. This includes defining whether a given patient is to receive real or sham stimulation. When the protocol has been defined it is downloaded to a Patient Key (USB memory device).

Maintenance of Randomization Codes: In order to use Active/Placebo (A/P) for different groups, an Excel spreadsheet with number series for operators and subjects (active stimulation as well as placebo stimulation) is stored by a separate clinical research coordinator who is trained to maintain the blind. Subjects codes (Randomization Stimulation Numbers) are followed by 0 or 1, where “0” is placebo stimulation and “1” is real stimulation.

Maintaining Appropriate Masking: All site personnel will be masked to the stimulation group assignment (active versus sham) for each subject. Specific aspects of the trial design are intended to optimize the integrity of the masking and all staff will be trained to the procedures for masking during the site initiation visit. In addition to those procedures, the treater will be provided with individually sealed and numbered envelopes, corresponding to subject randomization numbers.

Procedures for Planned and Unplanned Breaking of Randomization Codes: In the case of an emergency, an envelope may be opened to identify the TMS stimulation group assignment for a particular subject. In all circumstances, the Principal Investigator (PI) will notify NCCIH prior to unmasking the TMS stimulation group assignment for any subject, if possible. In the event that the emergency circumstances preclude first notifying NCCIH immediately, the PI will contact NCCIH within one business day and provide the reason(s) for unmasking and date of opening of the envelope must be documented in the subject’s files. The unmasking must also be documented on the Adverse Event page of the CRF, and in the subject’s source documents. Additionally, the PI will submit a written explanation describing the unmasking within 5 working days to NCCIH.

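### Section 9.3 has the principal investigator set real or sham for each patient yet calls all site personnel masked, and the protocol gives two times for randomisation; both need reconciling

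*Combined protocol and SAP*

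**What the plan says.** **Who sets the arm and who knows it.** In 9.3, under the randomisation procedure, the MagLink "software program is used by the principal investigator to define the stimulation protocol for each patient enrolled in the study". The next sentence is explicit: "This includes defining whether a given patient is to receive real or sham stimulation". The result is written to a USB Patient Key. Under the masking heading of the same section: "All site personnel will be masked to the stimulation group assignment (active versus sham) for each subject". No exception is attached.

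On the sequence, 9.3 says: "We perform randomization using permuted block to ensure balancing between arms". A spreadsheet carrying the arm codes "is stored by a separate clinical research coordinator who is trained to maintain the blind".

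Section 3 describes the coil as delivering active or sham "in a manner that is randomized by the system itself and therefore blinded to the treater". Under Continuous TBS Session it says: "The Magventure device holds a blinded key code that is kept by the unblinded CRC". Under Randomization and Blinding the holder becomes unspecific: "The Magventure TMS device holds a blinded key code that is kept by the individual that holds the blind". Later in 9.3, the key used for unmasking comes from the unblinded coordinator.

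**When randomisation happens.** The schedule in 6.1 marks enrolment and randomisation once, in the Visit 1 (Day 0) column. The Précis has the randomisation code assigned after full consent, before the imaging visits. Section 6.2.2 puts randomisation directly before stimulation, with stimulation following at once.

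**Rules that depend on the time.** Section 8 replaces subjects who withdraw before the scanner session. The washout paragraph of 9.1 reclassifies those who cannot tolerate washout as screen failures and replaces them. Section 9.4 compares participants as randomised under intention to treat.

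**The concern.** A person who decides real or sham for each patient knows the arm. If that person is the principal investigator, the sentence on masking is untrue for a role with several duties during the trial. Section 10.3.5 gives a principal investigator data verification and the review of questionnaires and neuroimaging, and Section 8 gives that role power to withdraw subjects. Those steps would not be masked.

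The general sentence in 9.3 carries real weight. Section 3 claims double blinding only for the treater and the participant. The SAP analyses change in the Hypnotic Induction Profile (HIP), which 6.2.1 describes as administered by a clinician. I found no statement naming the rater after stimulation or separately saying that the rater is masked. A reader who wants to know whether HIP was rated blind therefore depends on the general sentence, which should be true and should list its exceptions.

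The timing conflict decides who counts as randomised. A participant replaced before randomisation is a screening loss. The same participant replaced afterwards is a post-randomisation exclusion, which 9.4 does not allow for.

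**Working it through.** No arithmetic applies. The check sets the statements side by side.

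*Masking*

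1. Section 9.3 assigns to the principal investigator the definition of real or sham, patient by patient, in MagLink.
2. Section 9.3 states that every member of site personnel is masked to each subject's arm.
3. The principal investigator is site personnel, so 1 and 2 conflict unless the investigator loads coded keys without seeing the arm. No text says this, and the word defining in 9.3 points the other way.
4. Even on that softer reading, 2 fails as worded, because Section 3 and 9.3 both refer to an unblinded coordinator. Section 9.3 does disclose that a separate coordinator stores the codes, but the masking sentence does not exempt that role.
5. Evidence on intent: in 9.3 the principal investigator notifies the funder before any unmasking and weighs whether breaking the blind would change care; the key is obtained from the unblinded coordinator; and the Patient Keys return to the principal investigator only at study end. These steps make little sense if the investigator already knows every arm. The likely intent is a masked investigator.

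*Timing*

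1. Section 6.1: one mark, at Visit 1, and none on the target scan day or either stimulation day.
2. Précis: code assigned before the imaging visits. This agrees with 6.1, or at least does not contradict it.
3. Section 6.2.2: directly before stimulation. It does not say which of the two stimulation days, although Section 3 keeps one condition for both.
4. Section 9.6.1 mentions the pre-stimulation scan, then randomisation, then the later scan. That order is compatible with 6.2.2 but does not fix the time.

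*Consequence for the analysis set*

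- Randomisation at Visit 1: someone who withdraws between Visit 1 and the scanner has been randomised and is replaced under Section 8. The same applies to a washout failure under 9.1 if the washout runs after Visit 1. Both conflict with 9.4.
- Randomisation directly before the first stimulation: a washout failure or a withdrawal before the first scan has not been randomised, and replacement is consistent with 9.4.

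**The case against.** The strongest reply is that this is loose wording. The unmasking procedures presuppose a masked investigator, the code holder is disclosed in 9.3 itself, and the detailed blinding manual (Appendix 3) was not available for this review. Two principal investigators are listed, and the text does not show whether the one using MagLink does the checking in 10.3.5. Those duties are quality control, not outcome rating. The SAP also describes completed analyses, so editing the protocol cannot change conduct. All of this stands. It limits the claim, but it does not make the two sentences in 9.3 compatible.

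A reader might go further in four ways that the documents do not support.

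- *That the investigator was in fact unmasked and the results are biased.* Nothing shows this. No text says a principal investigator rates HIP, and 4.3 gives the HIP selection before randomisation to a trained team member.
- *That Section 3 describes a rival allocation method.* Randomisation by the system may describe blinded delivery of a permuted-block sequence generated elsewhere. The wording should be aligned, but two mechanisms are not established.
- *That 9.6.1 confirms the time in 6.2.2.* Only its sentence order suggests so.
- *That intention to treat was broken.* This arises only if randomisation is at Visit 1. A code assigned at Visit 1 and revealed at stimulation would reconcile the timing statements, but no text says that is the arrangement.

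**Conclusion.** Both inconsistencies are in the current text and should be corrected. On masking, 9.3 contradicts itself, and the unblinded coordinator is an unstated exception. On timing, the schedule and the Précis differ from 6.2.2, and the choice determines whether the replacement rules respect the as-randomised set.

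No size of bias is claimed and none can be derived. The masking consequence assumes that 9.3 is followed literally and that the investigator using MagLink also holds the duties in 10.3.5 or Section 8. The analysis-set consequence assumes randomisation at Visit 1. The SAP's chi-squared test of the blind does not resolve the matter, because the SAP does not say whose blind was tested. Confidence is medium: the contradictions are plain, but their practical effect is unknown.

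**What to change.** **Masking.** In 9.3, have the existing unblinded coordinator load the permuted-block list into MagLink and onto the Patient Keys. Name that role as the only exception to masking. State that the principal investigators, HIP raters, operators and imaging reviewers have no access to assignments before database lock except through the unmasking procedure. Make the two descriptions in Section 3 match.

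**Timing.** State one time, immediately before the first of the two stimulation sessions, in the Précis, 6.1 and 6.2.2. If instead a code is assigned at Visit 1 and revealed later, say so and count those participants as randomised. In Sections 8, 9.1 and 9.4, state that only participants not yet randomised are replaced and that everyone randomised is in the intention-to-treat set.

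**Report.** Because the SAP describes finished analyses, this is the most useful part. The report should say who loaded MagLink; who was unmasked, and whether any of them rated HIP, reviewed data or withdrew participants; when randomisation occurred; how many were randomised and how many replaced in each arm; and whose blind the chi-squared test assessed.

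**Cost.** Wording edits in the Précis and Sections 3, 6.1, 6.2.2, 8, 9.1, 9.3 and 9.4, and one short paragraph in the report. The unblinded coordinator already exists in the plan, so no extra staff, visits or participants are needed.

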9.4 Definition of Populations

We will compare individuals assigned to the active rTMS condition and individuals assigned to the sham condition as randomized in line with the ITT principle. Noncompliance with rTMS (or sham) is not expected, although in that case, we will compare groups as randomized regardless of the compliance status in line with ITT. Missing assessment due to unusable imaging data or dropout will be handled as missing at random conditional on observed information.

9.5 Interim Analyses and Stopping Rules

Because of the anticipated low level of adverse events of TMS and MRI, the IMC will be charged with reviewing adverse events at least every six months. Serious adverse events will be reviewed on a monthly basis, unless a more urgent review is requested. Only under extreme circumstances or if it were determined that a high level of side effects was due to TMS and/or MRI, would the IMC be charged with breaking the study mask. This study will be stopped prior to its completion if: [1] the intervention is associated with adverse effects that call into question the safety of the intervention; [2] difficulty in study recruitment or retention will significantly impact the ability to evaluate the study endpoints; [3] any new information becomes available during the trial that necessitates stopping the study; or [4] other situations occur that might warrant stopping the study.

9.6 Outcomes

9.6.1 Primary Outcomes

Primary Mechanistic Outcome Measure: *To determine the effect of active, inhibitory rTMS (cTBS) over L-DLPFC on modulating the connectivity of the neural network that underlies hypnotizability.*

This study will test an augmentation approach where one modality (rTMS) (30) is being used to modulate the neural circuitry underlying another technique (hypnotizability) in an effort that this combinatory approach may transiently produce the high hypnotizable phenotype on formal testing(31). It will be determined if modulation of the neural circuitry that underlies hypnotizability with rTMS can potentially produce a brain connectivity pattern that resembles a highly hypnotizable individual(31). This study proposes to measure the change in hypnotizability by contrasting the functional connectivity between the L-DLPFC and dACC at pre- and post-rTMS for both rTMS conditions (active versus sham cTBS) (31).

Hypnotizability Scans for Primary Outcome Measure: All participants will receive the same identical pre-rTMS resting state scan(31, 51). After randomization (to either active DLPFC rTMS or sham rTMS) where one half (n=45) will receive active DLPFC rTMS (cTBS), and one-half sham DLPFC rTMS (cTBS) (n=45)(30), all participants have their hypnotizability post-rTMS scan session(31, 51).

fMRI Preprocessing and Analysis: All fMRI data will be preprocessed and analyzed using FSL (FMRIB Software Library, version 5.0) (88). Physiological signals will first be removed using RETROICOR and RVHRCOR (97, 98). The first 6 volumes will be discarded to allow for signal stabilization. The following standard preprocessing steps will then be applied: motion correction using least square minimization (99), removal of non-brain tissues (100), resampling to 2 x 2 x 2 mm³ voxels, spatial smoothing with a 6 mm full-width at half-maximum (FWHM) Gaussian kernel to improve functional alignment between participants, and mean-based intensity normalization of all volumes by the same factor and high pass temporal filtering with a Gaussian-weighted least-squares straight line fitting, and linear registration using the FMRIB's Linear Registration Tool (FLIRT, 6 degrees of freedom (DOF)) to T1-weighted anatomical images and Montreal Neurological Institute (MNI) standard space.

For each run, a first-level general linear model (GLM) will be conducted using FMRIB's improved linear model prewhitening convolved using a boxcar regressor model (101). Across runs and for each contrast, a within-subject fixed effects analysis will be performed. For group analysis, FMRIB's local analysis of mixed effects will be used within a mask of our a priori ROIs dACC and L-DLPFC, thresholded using family-wise error (FWE) corrected $Z > 2.3$; cluster $p < 0.05$. Average contrast of parameter estimate values will be extracted from our ROIs and Spearman's correlations will be calculated between these values and differences in active versus sham rTMS.

Primary Mechanistic Hypothesis: *Active, inhibitory rTMS (cTBS) over L-DLPFC will modulate the neural network that underlies hypnotizability by producing greater increases in functional connectivity between DLPFC and dACC and reduced activity in both L-DLPFC and dACC.*

Connectivity between L-DLPFC and dACC will be assessed with resting state functional connectivity MRI (31, 51) at the baseline time-point and as well as at the post-rTMS time-point for both rTMS conditions (active and sham). It is hypothesized that inhibitory rTMS (cTBS) to DLPFC will result in increased fc between the DLPFC and dACC. Analyses will be restricted to the dACC and L-DLPFC for the Primary Outcome Measure. To determine if the active rTMS condition is specifically associated with change in dACC and DLPFC functional connectivity, a mask restricted to dACC and DLPFC will be utilized to extract the fMRI connectivity data. It is expected that the correlation in active rTMS group over L-DLPFC to be stronger than the correlation obtained in the sham rTMS group. Regression analysis will be used to investigate whether greater connectivity will be present between L-DLPFC and dACC for active versus sham rTMS (cTBS). Activity in both regions will be measured using the fractional amplitude of low-frequency fluctuation (fALFF) of the fMRI signal to measure the amplitude of regional spontaneous activity throughout the brain. (164) It is a ratio of the power spectrum of low-frequency (0.01-0.08 Hz) to that of the entire frequency range, thereby controlling for overall physiological noise.

Relevant Clinical Outcome: *To determine the effect of active, inhibitory rTMS over DLPFC on enhancing hypnotic analgesia.*

This aim explores if active rTMS + HA will have produce greater anti-nociceptive effects on pain thresholds than sham rTMS. Inhibitory rTMS (cTBS) will be applied to L-DLPFC and it is expected that the stimulation-induced augmentation of hypnotic analgesia will be greater in the active rTMS condition over the sham rTMS condition. It is expected that the strength of this correlation will be greater than in the active rTMS + HA condition versus sham rTMS + HA given that the hypothesis is that the rTMS will increase fc between L-DLPFC and dACC which is believed to transiently modulate these participants to have similar response to hypnotic analgesia as do high hypnotizables(31) given the 0.6 correlation between measured hypnotizability and the ability to achieve hypnotic analgesia. HA network activation/connectivity to painful thermal stimulation will be assessed at baseline, during pre-rTMS hypnotic analgesia, after rTMS, and during post-rTMS HA. Changes in mean pain ratings between baseline pain and active rTMS + HA (TBS) and sham rTMS + HA conditions will be compared using ANOVA. It is expected that there will be a significantly greater mean decrease in pain ratings with the active rTMS + HA than the sham rTMS + HA condition at the $p < 0.05$, level.

Relevant Clinical Hypothesis: *Active, inhibitory rTMS over DLPFC will enhance hypnotic analgesia as compared to sham rTMS.*

It is hypothesized that the rTMS modulation in hypnotizability(26) will result in greater hypnotic analgesia than sham rTMS. It is expected that a significantly greater mean increase across measures active rTMS than with the sham rTMS condition at the $p < 0.05$, level. This hypothesis will be tested with linear mixed modeling. It is hypothesized that the rTMS modulation will result in greater analgesia than sham rTMS. This study will measure the response to thermal pain stimuli at baseline and after active rTMS versus sham rTMS. In particular, it is hypothesized that the temperature necessary to produce threshold level heat pain during the pre-TMS period will not produce pain following active rTMS + HA. The temperature for evoking threshold and moderate pain will be assessed prior to and at 5-minute intervals for 30 minutes following the application of rTMS + HA. It is expected that the active rTMS stimulation + HA will temporarily eliminate pain following thermal stimulation at an intensity, which produced threshold level pain prior to rTMS + HA. It is also hypothesized that temperatures that produced moderate pain prior to rTMS will be significantly reduced following active rTMS versus sham. This hypothesis will be tested with linear mixed modeling and changes $p < .05$ are considered statistically significant.

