Data Collected to Assess Safety During rTMS: Treaters will be monitoring subjects for the potential development of seizures by continuous visual inspection during the course of each stimulation session (especially the more subtle signs and symptoms of frontal lobe seizures), and first responder management in the event of a seizure. The study personnel have immediate (i.e., within minutes) availability of more sophisticated medical support, including access to an emergency room, in the event that a seizure is not a self-limited event, access to antiepileptic medications, and to life support equipment including oxygen, suction, blood pressure monitoring and cardiopulmonary (CPR) equipment.

Seizure and the following are AE's that will be reported at solicited events:

Body System - Preferred Term	Active TMS (N=165) N (%)	Sham TMS (N=158) N (%)
Eye disorders - Eye pain	10 (6.1)	3 (1.9)
Gastrointestinal disorders - Toothache	12 (7.3)	1 (0.6)
General disorders and site administration conditions - Application site discomfort - Application site pain - Facial pain	18 (10.9) 59 (35.8) 11 (6.7)	2 (1.3) 6 (3.8) 5 (3.2)
Musculoskeletal and connective tissue disorders - Muscle twitching	34 (20.6)	5 (3.2)
Skin and subcutaneous tissue disorders - Pain of skin	14 (8.5)	1 (0.6)

Table 2: Adverse events with an incidence in active rTMS at a rate of > 5% and at least 2x sham in the safety exposure study population. These symptoms have occurred only during and not after rTMS administration.

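### As written, the primary connectivity pipeline uses one rigid 6-DOF fit for both T1 and MNI space and sets no motion control beyond realignment and physiological noise removal

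*Combined protocol and SAP*

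**What the plan says.** All references are to the combined protocol and SAP unless stated.

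- **Registration (9.6.1, fMRI Preprocessing and Analysis).** One FLIRT step is described: "6 degrees of freedom (DOF)) to T1-weighted anatomical images and Montreal Neurological Institute (MNI) standard space". A single degrees-of-freedom figure covers both targets. No 12-DOF affine or nonlinear step is mentioned in either document.
- **Smoothing (same paragraph).** "spatial smoothing with a 6 mm full-width at half-maximum (FWHM) Gaussian kernel to improve functional alignment between participants", on 2 mm voxels.
- **Noise and motion (same paragraph).** "Physiological signals will first be removed using RETROICOR and RVHRCOR (97, 98"), followed by volume realignment: "motion correction using least square minimization (99").
- **First-level model (9.6.1).** "improved linear model prewhitening convolved using a boxcar regressor model (101"). No nuisance regressor is named.
- **Extraction of the primary value (9.6.1, Primary Mechanistic Hypothesis).** "a mask restricted to dACC and DLPFC will be utilized to extract the fMRI connectivity data". How the mask is built is not stated.
- **Primary model (9.2).** The pre/post contrast is a single outcome regressed on arm alone.
- **Unusable scans (9.2, 9.4).** About 20% of participants are expected to be lost to unusable images or dropout. These losses are treated as missing at random, and no motion criterion defines an unusable scan.

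The separate SAP dated January 4, 2024 covers only the hypnotizability score and the test of blinding, so it adds nothing on imaging.

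**The concern.** A 6-DOF transform rotates and translates but does not scale. That suits aligning a functional image to the same person's T1. It does not fit one brain to a template of a different size. If it is the only step to MNI space, a region defined on the template can fall partly outside the intended cortex. The extracted connectivity then mixes in other tissue and the contrast between arms shrinks.

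The second gap concerns movement. Realignment puts volumes back in register, and RETROICOR/RVHRCOR remove cardiac and respiratory signal. Neither removes the signal change that head movement leaves after realignment. Such residual signal can alter a correlation between two regions. The post-stimulation scan follows the randomised intervention, so randomisation does not guarantee equal movement there. With no motion term in the preprocessing, the first-level model or the group model, a difference in movement cannot be told apart from a difference in connectivity. This falls on the primary mechanistic test.

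**Working it through.** **1. The plan's own figure.** Section 9.2 gives d = 0.8, 40 usable per arm, two-sided alpha 0.05 and power 0.8. The noncentrality is d × √(n/2) = 0.8 × √20 = 3.58, and the noncentral t with 78 df gives power 0.942 (normal approximation 0.947). The stated 0.8 is not reproduced. Power of 0.80 at 40 per arm corresponds to d = (1.960 + 0.842) × √(2/40) = 0.63. That mismatch is a separate matter and errs on the safe side. The recomputed 0.942 is the reference below. The recruitment step does reproduce: 80/(1 − 0.2) = 100.

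**2. Displacement under a rigid fit.** The documents give no head-size data, so the mismatch *s* and the distance *r* from the alignment centre are assumed. Displacement = s × r.

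| s | r = 30 mm | r = 50 mm | r = 70 mm |
|---|---|---|---|
| 5% | 1.5 mm | 2.5 mm | 3.5 mm |
| 10% | 3.0 mm | 5.0 mm | 7.0 mm |
| 15% | 4.5 mm | 7.5 mm | 10.5 mm |

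Against a 6 mm kernel, the smaller values would be largely absorbed and the larger ones would not.

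**3. What dilution would cost.** The documents do not link millimetres to loss of effect, so the dilution fraction is also assumed. Power is for 40 per arm (noncentral t).

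| Dilution | Remaining d | Power |
|---|---|---|
| 0% | 0.80 | 0.942 |
| 10% | 0.72 | 0.889 |
| 20% | 0.64 | 0.807 |
| 30% | 0.56 | 0.696 |
| 40% | 0.48 | 0.564 |

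The margin is thinner at d = 0.69, the value section 9.2 takes from the one cited DLPFC–dACC study. Power there is 0.862 undiluted. Dilution of about 9% (0.63/0.69 = 0.91) brings it to 0.795.

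**4. What differential movement would cost.** Suppose there is no true effect, but residual motion shifts the between-arm difference in change by *b* SD (assumed). The rejection rate is the power function evaluated at d = b.

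| b | Two-sided false-positive rate |
|---|---|
| 0 | 0.050 |
| 0.1 | 0.073 |
| 0.2 | 0.143 |
| 0.3 | 0.263 |
| 0.5 | 0.598 |

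These figures show sensitivity only. Nothing in the documents says which *b*, if any, applies, or its sign.

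**5. Whether the citations settle the text.** The preprocessing text in 9.6.1 cites references 88 and 97–101. In section 14 these are a TMS safety questionnaire, a review of TMS seizure risk, a hypnotizability paper, TMS safety guidelines, a drug–TMS interaction study and a TMS–antidepressant trial. None is an imaging-methods source, so the citations cannot show which registration or motion steps were meant.

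**The case against.** Several counterarguments carry weight.

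- **The 6 DOF may be compressed wording.** One clause covers two registrations, and the figure may belong only to the functional-to-T1 step. This stands. The T1-to-MNI method is then simply unstated and still has to be written.
- **The masks may not be template masks.** Sections 3 and 6.2.2 take the stimulation target from each participant's own connectivity peak, and the extraction masks might be individual too. A reader might infer that the masks are off target; the documents do not establish that. The group analysis within a priori regions still needs a common space.
- **Misregistration is largely shared** by a person's pre and post scans and does not depend on arm. This stands. It mainly dilutes, and recomputed power stays at about the planned 0.8 after 20% dilution of d = 0.8.
- **Movement is not ignored.** A reader might infer that the pipeline does nothing about it, but realignment and physiological correction are specified. The boxcar model describes task data, and resting-state connectivity is described separately with citations unavailable here. Not stated is not the same as not done. Even so, leaving the choice open on a primary outcome allows it to be made after the data are seen.
- **The adverse-event table in 7.3 does not show a difference in movement.** Its application-site pain rates (59/165 = 35.8% active, 6/158 = 3.8% sham) invite the inference that the active arm would move more in the later scan. The caption limits these symptoms to the stimulation itself, and the outcome scan comes afterwards. The rates also come from a population of 165 + 158, not this trial's 100. The table should not be used for this argument.

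**Conclusion.** The point holds as a gap in the specification of the primary outcome. It does not show that the primary result is biased.

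On registration, the literal text fits brains to the template without scaling. The likely consequence is loss of power with little preference for either arm: from 0.94 to about 0.81 or 0.70 for assumed dilutions of 20% or 30% at d = 0.8. This rests on the literal reading, on template-space masks and on assumed mismatch.

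Motion is the more important part, because it could favour an arm. Differential movement is conceivable. Participants have chronic pain and suspend analgesics for 24 hours before scans (4.1), which applies to both arms, while active stimulation is hypothesised to alter hypnotic state and analgesia (1.1). No figure in the documents supports a particular size or direction.

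This should be fixed before the imaging data are analysed. It is not severe enough to call the design into question.

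**What to change.** In section 9.6.1:

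1. State the registration steps separately: 6-DOF or boundary-based for functional to T1, and 12-DOF affine plus nonlinear for T1 to MNI. Say how the dACC and L-DLPFC masks are defined and in which space.
2. For resting scans, add the realignment parameters with their derivatives, and white-matter and CSF signals, as nuisance regressors.
3. Prespecify the motion limit that makes a scan unusable, and refer to it in 9.4.
4. Report mean displacement by arm and time point.
5. Add two sensitivity analyses: one with censoring of high-motion volumes and one with change in displacement as a covariate. Censoring belongs here rather than in the main analysis because its threshold is debatable. The covariate is measured after randomisation, so that model should not replace the primary one.
6. Correct the reference numbers in the preprocessing text.

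The cost is small. These are settings in or around the software already named (FSL) and need no new data. Some temporal degrees of freedom are lost per run, and a few more scans may fail quality control.
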